4.1.3 Analysis Populations

The analysis populations defined for this study are presented in [Table 4-1](#).

Table 4-1 Analysis Populations

Population	Definition / Criteria	Analyses Evaluated
Safety	Comprise all randomized subjects who receive at least one dose of the study product. Any subject who receives a randomization number will be considered to have been randomized. This population will be based on the study product the subject actually received.	Safety Analysis
Modified Intent-To-Treat (mITT)	Comprise all randomized subjects who receive at least one dose of the study product and provide at least one post-baseline assessment of efficacy (Schiff sensitivity assessment or Tactile sensitivity assessment). Any subject who receives a randomization number will be considered to have been randomized. This population will be based on the study product to which the subject was randomized.	Demographic and Baseline Characteristics, Efficacy Analysis
PP	Comprise all subjects included in the mITT population who have at least one assessment of efficacy (Schiff sensitivity assessment or Tactile sensitivity assessment) considered unaffected by protocol violations.	Efficacy Analysis

NOTE:

Please refer to [Attachment 1](#): List of Data Displays which details the population to be used for each displays being generated.

The primary population for assessment of efficacy will be the mITT population. A PP analysis will be performed on the primary and secondary variables (Schiff score and Tactile threshold)

Stannous fluoride (SnF₂)
216954

if there is more than 10% difference in the number of subjects between the PP and mITT population. A decision will be made to perform PP analysis after the BDRM but prior to study unblinding (release of the randomization codes).

The numbers of subjects included in each of the analysis populations will be presented in [Table 14.1.1](#) by study product and overall. Subjects excluded from any of the analysis populations will be listed in [Listing 16.2.3.1](#) by study product.

4.2 Subject Demographics and Other Baseline Characteristics

4.2.1 Demographic Characteristics

Descriptive statistics (number of subjects [n], mean, SD, median, minimum and maximum for continuous variables and frequency count [n] and percentage [%] of subjects for categorical variables) will be presented for demographic variables and baseline characteristics by study product and overall. These variables include age, gender, race, ethnicity and baseline Schiff stratification score, and will be presented for Safety and mITT populations ([Table 14.1.3.1](#) and [Table 14.1.3.2](#), respectively) and PP population ([Table 14.1.3.3](#)) if criteria for PP analysis is met.

Demographic and baseline characteristics information will be listed ([Listing 16.2.4.1](#)) for all randomized subjects by study product.

4.2.2 General Medical History

Since results will be reported in a synopsis CSR, collected data for Medical history will not be tabulated or listed.

4.3 Treatments (Study Product, Rescue Medication, other Concomitant Therapies, Compliance)

Randomization details will be listed, including the randomization number, stratification group, planned study product, actual study product and the randomization date ([Listing 16.1.7.1](#)).

The study product kit allocations will be listed ([Listing 16.1.7.2](#)), including kit number and study product information.

4.3.1 Study Product Compliance and Exposure

Study product compliance data will be summarized for the mITT population and will be assessed by:

- Number of brushings
- Study dentifrice weight

Stannous fluoride (SnF₂)
216954

Number of brushings, brushing compliance (%), number of missed brushings, number of additional brushings and amount of product used (g) will be summarized using descriptive statistics as separate categories by study product in [Table 14.2.1.1](#) by visit and overall.

Number of brushings is defined as: [(date of Visit_n – date of Visit_{n-1} + 1) multiplied by 2 – number of missing brushings + number of additional brushings] by visits, and [(date of Visit 4 – date of Visit 2 + 1) multiplied by 2 – number of missing brushings + number of additional brushings] by overall.

Brushing compliance (%) is defined as: [100 x (Number of brushings / Expected number of brushings)], where expected number of brushings is defined as: [(date of Visit_n - date of Visit_{n-1} + 1) multiplied by 2] by visits, and [(date of Visit 4 – date of Visit 2 + 1) multiplied by 2] by overall.

Study product compliance (number of brushings / brushing compliance [%] / number of missed brushings / number of additional brushings / amount of product used [g]) will be listed in [Listing 16.2.5.1](#) for all randomized subjects by study product.

Supervised study product brushings will also be summarized for the mITT population in [Table 14.2.1.2](#) by visit. In addition, details (including subject number, date and start time of supervised brushing) for supervised study product brushings will be listed ([Listing 16.2.5.2](#)) for all randomized subjects by study product.

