5.5 Lifestyle Considerations

5.5.1 Oral Care Restrictions

Eligible subjects will be asked to stop using their regular oral care products, and will only be allowed to use the oral care products provided from Screening for the duration of the study. Use of dental floss will be for the removal of impacted food only.

Subjects will not be permitted to chew gum.

Prior to study visit days (Visits 2 to 4) subjects will be asked to refrain from all oral hygiene procedures for at least 8 hours prior to their appointment in order to standardise oral hygiene

practices. Subjects will be sent a WeChat reminder the day before their appointment reminding them of this.

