6.4 Investigational/Study Product Accountability

All products supplied are for use only in this clinical study and should not be used for any other purpose.

Property of GSK Consumer Healthcare - Confidential

May not be used, divulged, published or otherwise disclosed without the consent of GSKCH

SOP-208661 Clinical Protocol Template v6.0

Page 34 of 85

All study products must be received by a designated person at the study sites, handled and stored safely and properly, and kept in a secured location to which only the staff have access. Upon receipt, all study products should be stored according to the instructions specified on the product labels. Study products are to be dispensed only to subjects enrolled in the study in accordance with the protocol, by authorised site staff.

The investigative site must maintain adequate records documenting the receipt, use, loss, or other disposition of all the product supplies. All study products will be accounted for using the investigational/study product accountability form/record. The investigator is responsible for study product accountability, reconciliation, and record maintenance.

Subjects will return used and unused tubes of the acclimatisation dentifrice to the investigator site at their Baseline visit (Visit 2). Subjects will return used and unused tubes of their assigned study dentifrice to the investigator site at their visits to the clinical study site as per the Schedule of Activities, with all study products returned at the end of the study (for most subjects this will be Visit 4). Study product return will be documented using the investigational/study product accountability form/record.

The accountability records must be available for inspection by the study monitor during the study. Monitoring of product accountability will be performed by the monitor during site visits and at the completion of the study.

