8.2.2.8 Supervised Brushing with Randomised Dentifrice

At Visit 3 subjects will be instructed to perform a supervised and timed brushing according to the product usage instructions, as detailed in [Table 6-1](#). Confirmation of supervised brushing per protocol will be captured in the CRF and an entry recorded on the subject diary card. Any deviations from the product usage instructions will be captured as a protocol deviation, and subjects will be reminded of the correct directions for use.

Subjects will be re-dispensed a new toothbrush at Visit 3 and reminded to bring their study products to their next clinical study site visit.

Note: this is only applicable at Visit 3, and is not required at Visit 4.

Property of GSK Consumer Healthcare - Confidential

May not be used, divulged, published or otherwise disclosed without the consent of GSKCH

SOP-208661 Clinical Protocol Template v6.0

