12.3.7 Study Product Compliance and Use of Other Therapies

12.3.7.1 Study Product Compliance

This will be assessed by:

- Number of brushings
- Study dentifrice weight

The number of brushings and corresponding compliance rate will be summarised by treatment group between treatment visits and across the whole duration.

Number of brushings compliance will be calculated as :-

Property of GSK Consumer Healthcare - Confidential

May not be used, divulged, published or otherwise disclosed without the consent of GSKCH

SOP-208661 Clinical Protocol Template v6.0

$100 \times (\text{number of actual brushings}) / (\text{number of expected brushings})$

Number of expected brushings = $2 \times \text{number of days between Visit}_n \text{ and Visit}_{n-1}$

For the study dentifrice weight, the study dentifrice will be weighed at each visit. the pre-defined range will be calculated as the expected weight of toothpaste used for the treatment window. E.g. $(2\text{g} \times 28 \text{ days}) \pm 40\%$, therefore, in a 4 week treatment period the expected amount of toothpaste used would be $\geq 33.6\text{g}$ and $\leq 78.4\text{g}$. The amount of dentifrice used during each treatment period will be recorded in a source document and later transcribed to the CRF.

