4.1 Populations for Analysis

4.1.1 Subject Disposition

Screen failures are defined as subjects who consent to participate in the clinical study but are not subsequently randomized. An enrolled subject is a subject who has signed informed consent and is eligible to proceed beyond the screening visit.

Stannous fluoride (SnF₂)
216954

The number of subjects screened, subjects not randomized, and subjects enrolled will be presented for all screened subjects in [Table 14.1.1](#).

[Table 14.1.1](#) will also display the number and percentage of screen failure subjects (subjects not randomized) with reasons why subjects are not randomized. Percentages for screen failure subjects will be based on the total number of subjects screened.

The number and percentage of subjects randomized, who complete the study and who discontinue the study broken down by reason for discontinuation, by study product and overall will also be displayed. The percentages will be based on the total number of subjects randomized.

[Table 14.1.1](#) will also present the number and percentage of subjects in each of the defined analysis populations by study product and overall. Percentages will be based on the number of subjects randomized.

Subject disposition including demographic data (age, sex and race), screening date, study product start date and time, study product end date and time, duration of study product in days (defined as [(last date of study product administration - start date of study product) + 1] for all subjects completing the study as per protocol, and [(date of withdrawal - start date of study product) + 1] for all subjects dropping out of the study), subject status (completer, Yes/No), study completion/withdrawal date, duration in the study in days (defined as [(date of completion or withdrawal - start date of study product) + 1], and the primary reason for withdrawal will be listed ([Listing 16.2.1.1](#)) by study product for all randomized subjects.

Subject disposition information will be listed for non-randomized subjects ([Listing 16.2.1.2](#)), displaying subject number, demographic information (age, sex and race), screening date, reason for screen failure and any further details of reason for screen failure.

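### SAP 4.3.1 adds a day to every brushing interval, so a completer's by-visit expected brushings sum to 2 more than the overall figure (116 v 114 at nominal days; 112 under the protocol rule)

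*SAP*

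**What the plan says.** Protocol 12.3.7.1 defines expected brushings as twice the "number of days between Visit" n and the visit before it. The same section works an example of dentifrice weight in which a 4-week period is 28 days.

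SAP 4.3.1 adds one day to the date difference before doubling, both for each by-visit interval and for the period from Visit 2 to Visit 4: "date of Visit 4 – date of Visit 2 + 1) multiplied by 2". The added day appears in the number of brushings (scheduled brushings, minus missed, plus additional) and in the expected number used as the denominator of compliance. Table 14.2.1.1 reports these by visit and overall. SAP Table 5-1, which is meant to list departures from the protocol analysis, has an entry for 12.3.7.2 but none for 12.3.7.1.

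Three protocol provisions bear on the last day. Subjects must "refrain from all oral hygiene procedures for at least 8 hours prior to their appointment" (5.5.1). For the supervised brushing, "this is only applicable at Visit 3, and is not required at Visit 4" (8.2.2.8). Product is handed back, "with all study products returned at the end of the study (for most subjects this will be Visit 4") (6.4).

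On population, SAP 4.6 places safety data, with exposure named among them, on the Safety population by product received. SAP 4.6.2 then sends the reader to 4.3.1 for exposure, where "Study product compliance data will be summarized for the mITT population".

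**The concern.** The two SAP formulas do not agree with each other. Each by-visit interval includes both of its end days, so the Visit 3 day is counted once as the end of the first interval and again as the start of the second. The overall formula counts it once. By-visit and overall figures in the same table will therefore not reconcile, even if the protocol is set aside.

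The overall formula also differs from the protocol by one day, the day of Visit 4, and the departure is not declared. What is at stake is the accuracy of a reported adherence measure, which SAP 4.6.2 also uses to describe exposure. The efficacy and adverse event analyses do not use it.

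**Working it through.** **Inputs.** Visit 2 is Day 1 (protocol 8.2.1). Visits 3 and 4 are Day 29±3 and Day 57±3 (protocol 8.2.2). Brushing is twice daily. The brushing counts below are derived; neither document prints them.

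**The protocol's own figure.** For 4 weeks, 2 g × 28 days = 56 g. Then 56 × 0.6 = 33.6 g and 56 × 1.4 = 78.4 g. Both match the printed range, so the protocol takes a 4-week interval as 28 days.

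**Expected brushings at nominal days.**

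| Rule | Visit 2–3 | Visit 3–4 | Sum | Overall |
|---|---|---|---|---|
| Protocol, 2 × difference | 2 × 28 = 56 | 2 × 28 = 56 | 112 | 2 × 56 = 112 |
| SAP, 2 × (difference + 1) | 2 × 29 = 58 | 2 × 29 = 58 | 116 | 2 × 57 = 114 |

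**Any visit dates.** 2(V3 − V2 + 1) + 2(V4 − V3 + 1) = 2(V4 − V2 + 1) + 2. The gap is 2 for every completer. Every combination of days within the ±3-day windows was also checked and gave 2.

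**Which days hold scheduled brushings.** Days 1–28 give 56 and Days 29–56 give 56, total 112. Day 1 is already inside the plain date difference. The extra day in the overall formula is Day 57, when pre-visit hygiene is restricted, no supervised brushing is required and product is returned.

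**Comparison with SAP 4.1.1.** For completers, duration is "last date of study product administration - start date of study product", plus 1. That + 1 is right because the end point is a day of use. Assuming last use on Day 56, (56 − 1) + 1 = 56 days, or 112 brushings. SAP 4.3.1 carries the + 1 over to a visit date.

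**Relative size of the excess in the scheduled count.**
- Nominal: 2/56 = 3.6% per interval; 2/112 = 1.8% overall.
- Visit 2–3, 25 to 31 days: 2/50 = 4.0% down to 2/62 = 3.2%.
- Visit 3–4, 22 to 34 days: 2/44 = 4.5% down to 2/68 = 2.9%.
- Overall, 53 to 59 days: 2/106 = 1.9% down to 2/118 = 1.7%.

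**Effect on compliance %,** if no Visit 4-day slot is recorded as missed. With E expected brushings under the protocol, each net missed brushing shifts the percentage by 100 × 2 / [E(E + 2)]. This is 200/(56 × 58) = 0.062 points per interval and 200/(112 × 114) = 0.016 points overall.

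| Net missed in 4 weeks | SAP | Protocol | Difference (points) |
|---|---|---|---|
| 6 | 52/58 = 89.7% | 50/56 = 89.3% | 0.4 |
| 10 | 48/58 = 82.8% | 46/56 = 82.1% | 0.6 |
| 17 | 41/58 = 70.7% | 39/56 = 69.6% | 1.05 |

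**If both Visit 4-day slots are recorded as missed.** A fully adherent subject has 114 − 2 = 112 brushings overall, which is the right number, but compliance reads 112/114 = 98.2%. By visit the counts are 58 and 58 − 2 = 56, sum 114, still 2 above the overall 112.

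**The case against.** A reader might infer that every reported number of brushings is too high by exactly 2. The documents do not support that. The number is net of missed brushings taken from the diary, and neither document says whether unused slots on the Visit 4 day are entered as missed. If they are, the overall number is right and the error moves into the percentage. An 8-hour abstention also leaves room for a morning brushing before a late visit, which would cut the overall excess to 1. In addition, protocol 4.2 and 6.7 speak of a supervised brushing at each visit. Section 8.2.2.8 is the more specific text and excludes Visit 4, but the wording is not uniform. All of this limits the claim about the reported number. None of it touches the 116 v 114 mismatch in expected brushings.

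A reader might also infer that treated subjects outside mITT have no exposure data. That is not so. Listing 16.2.5.1 (compliance) and Listing 16.2.1.1 (duration of study product) cover all randomised subjects, and Listing 16.1.7.1 gives the product actually received. What is not visible is a Safety-population summary. Attachment 1, which assigns a population to each display, is redacted and may contain one.

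Finally, the consequence is small. Neither document sets a brushing-compliance percentage cut-off. Non-compliance is judged on videos and dentifrice weight.

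**Conclusion.** The inconsistency is real and minor. The expected counts in SAP 4.3.1 contradict each other by 2 for every completer, whatever the visit dates. They also exceed the protocol rule by 2 per interval and 2 overall, and Table 5-1 does not record the departure. This much is exact. The reported number of brushings is overstated by up to 2, subject to the diary and visit-time conditions above, and its by-visit sum reconciles with the overall figure only if the formula is corrected (assuming that each missed or additional brushing is assigned to one interval). The compliance percentage changes by less than 1 point until about 17 net misses in a 56-brushing interval. No efficacy or adverse event result changes.

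The population question is a request for confirmation, not a demonstrated gap, because it rests on the visible text alone.

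**What to change.** In SAP 4.3.1, delete the + 1 from the by-visit formulas and from the Visit 2 to Visit 4 formulas, for both the number of brushings and the expected number. At nominal days this gives 56 + 56 = 112 by visit and 112 overall, in line with protocol 12.3.7.1. Declaring the change in Table 5-1 alone would leave two figures in Table 14.2.1.1 that do not add up. The cost is one formula edit.

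Separately, confirm that an exposure summary is produced for the Safety population by product received, keeping mITT for adherence. If Attachment 1 already assigns one, a clearer cross-reference in SAP 4.6.2 is enough.

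Do not import the SAP 4.1.1 rule for dropouts ("date of withdrawal - start date of study product) + 1") into 4.3.1 as an end date. Under protocol 7.2, loss to follow-up is declared only after repeated missed visits and contact attempts, so the withdrawal date can fall well after last use and overstate exposure.

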4.3.2 Prior and Concomitant Medication

Any medications, treatments or vaccine (including over-the-counter or prescription medicines, vitamins, and/or herbal supplements) taken during the study, from signing the informed consent, must be recorded in the CRF with indication, reason for use, unit dose, daily dose, and start and stop dates of administration. All subjects will be questioned about medications/treatments at each site visit.

Medication/treatments taken within 30 days of signing the ICF will be documented as a prior medication/treatment. Medications/treatments taken after signing the ICF will be documented as concomitant medication/treatments.

Since results will be reported in a synopsis CSR, collected data for Prior and Concomitant Medications will not be tabulated or listed.

4.4 Analysis of Efficacy

The mITT population will be considered as primary population for primary analyses.

Stannous fluoride (SnF₂)
216954

4.4.1 Primary Efficacy Endpoint

4.4.1.1 Primary Efficacy Endpoint Definition

The primary efficacy variable is the change from baseline in Schiff sensitivity score at 8 weeks, derived as the average score of the 2 test teeth. The change from baseline is derived from the individual teeth first before calculating the average change of the 2 test teeth.

Descriptive statistics (n, missing, mean, SD, standard error [SE], median, minimum, and maximum) will be presented for Schiff sensitivity score calculated as the average score of the 2 test teeth at each assessment time point together with the change from baseline in [Table 14.2.2.1.1](#) for all subjects in mITT population by study product. Raw means (\pm SE) of the Schiff sensitivity score at each time point will be plotted by study product in [Figure 14.2.1](#) for all subjects in mITT population.

4.4.1.2 Statistical Hypothesis, Model, and Method of Analysis

The primary comparison is between the test product and the negative control. As there is only a single primary objective no adjustment for multiple comparisons is required.

Study product differences will be tested under the null hypothesis:

- H_0 : there is no difference between test product and negative control;
- H_1 : there is a difference

Change from baseline in Schiff sensitivity score at 8 weeks will be analyzed using analysis of covariance (ANCOVA) with study product as a factor and baseline Schiff sensitivity score as a covariate. Note that since the baseline Schiff sensitivity score will be included as a covariate, the baseline Schiff stratification value will not be included in the model.

Using the above model, adjusted mean change from baseline, along with 95% confidence intervals (CIs) will be reported by study product. P-values testing for non-zero change from baseline will be presented for both study products. Mean difference between study products, 95% CIs and p-values will be provided for Schiff sensitivity score in [Table 14.2.2.1.2](#). Significance testing will be conducted at the two-sided 5% significance level; no adjustment for multiple comparisons will be made.

The assumption of normality and homogeneity of variance in the ANCOVA model will be investigated. In case of violation of these assumptions a suitable transformation or a non-parametric method (e.g. the van Elteren test), adjusting for the maximum baseline Schiff Sensitivity scores will be performed and results will be compared with the ANCOVA results.

4.4.1.3 Supportive Analyses

If there is more than 10% difference in the overall number of subjects between PP and mITT populations, a summary and analysis of the primary efficacy variable will be presented for the PP population in [Table 14.2.2.2.1](#) and [Table 14.2.2.2.2](#), respectively.

Stannous fluoride (SnF₂)
216954

